12.2 Participant demographics and other baseline characteristics

Demographics and other baseline characteristics will be summarized descriptively.

Relevant medical histories and current medical conditions at baseline will be summarized by system organ class and preferred term.

12.3 Treatment

The duration of exposure in days will be summarized descriptively.

Concomitant medications and significant non-drug therapies prior to and after the start of the study treatment will be listed and summarized according to the Anatomical Therapeutic Chemical (ATC) classification system.

12.4 Analysis of primary endpoint(s)/estimand(s)

The primary objective of this study is to characterize those achieving seroprotection after receiving the 2020-2021, 2021-2022, or 2022-2023 seasonal quadrivalent influenza vaccine in subjects treated with ofatumumab 20 mg sc once every 4 weeks. This will be achieved by estimating the seroprotection response rate.

A seroprotection responder is a participant achieving seroprotection as defined by a postvaccination antibody titer ≥ 40 .

The seroprotection response rate is defined as the proportion of subjects with seroprotection.

12.4.1 Definition of primary endpoint(s)/estimand(s)

The primary endpoint is achieving seroprotection as defined by a postvaccination antibody titer ≥ 40 (yes/no) at Week 4.

12.4.2 Statistical model, hypothesis, and method of analysis

The number and percentage of responders by year of enrolment in study and overall will be presented. The 95% confidence interval for the proportion of responders will be calculated by using exact method.

12.4.3 Handling of remaining intercurrent events of primary estimand

Not applicable.

12.4.4 Handling of missing values not related to intercurrent event

Non-responder imputation approach will be applied to missing postvaccination antibody titer.

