Investigation type	Biological/Vaccine	
Study type	Interventional, 3-cohort arm	
Purpose and rationale	The objective of this study is to assess whether participants treated with ofatumumab 20 mg subcutaneous (s.c.) administered once every 4 weeks (q4) can mount an adequate immune response to inactivated influenza vaccine as measured by humoral responses compared to participants on an iDMT.	
Primary Objective(s)	To characterize those achieving seroprotection to the 2020-2021, 2021-2022, or 2022-2023 seasonal quadrivalent influenza vaccine in participants treated with ofatumumab 20 mg sc once every 4 weeks.	
Secondary Objectives	To characterize those achieving seroconversion after receiving the 2020-2021, 2021-2022, or 2022-2023 seasonal quadrivalent influenza vaccine in participants treated with ofatumumab 20 mg sc once every 4 weeks	
	Safety	
Study design	This is a three cohort, multicenter, prospective study of up to 66 relapsing MS participants. The first cohort will be participants who will received 2020-2021, 2021-2022, or 2022-2023 inactivated influenza vaccine at least two weeks prior to ofatumumab start. The second cohort will be participants who will receive a 2020-2021, 2021-2022, or 2022-2023 inactivated influenza vaccine at least four weeks after beginning ofatumumab. The third cohort will be participants currently on an iDMT who will receive a 2020-2021, 2021-2022, or 2022-2023 inactivated influenza vaccine. All groups will undergo an HI titer prior to vaccination and then again four weeks after vaccination. Upon completing the study, participants in cohort 1 and 2 will have the option to continue into a 6 month open-label Extension Period.	
	Participants will obtain the quadrivalent influenza vaccine at no cost from their local pharmacy using a pharmacy card supplied by Novartis or from investigational site supply. Participants should receive the vaccine within 9 calendar days after the Screening Visit, before the Week 0 Visit occurs.	
Study population	Adult (ages 18-55) relapsing MS participants	
Key Inclusion criteria	 Written informed consent for the study must be obtained before any study assessment is performed Age 18-55 years old 	
	Diagnosis of relapsing MS by 2017 revised McDonald criteria	

	4. Must be willing to comply with the study schedule
	5. Willing to receive a 2020-2021, 2021-2022, or 2022-2023 inactivated influenza vaccine

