4.3 Rationale for choice of control drugs (comparator/placebo)

Since the ability to mount an immune response varies depending on the influenza strain administered, a reference cohort of participants on iDMTs (interferon or glatiramer acetate) is included. In a prior study, interferon and glatiramer acetate did not diminish influenza vaccine response (Olberg et al 2018.)

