12.8 Sample size calculation

12.8.1 Primary endpoint(s)

The sample size of 20 participants per arm is selected based on budget and need for early availability of results for the current influenza season. This sample size of 20 subjects will provide estimates of proportion responded with margin of error (half-width of a 95% confidence interval) of 20.1%, 19%, and 17.5% corresponding to response rates of 70%, 75%, and 80%, respectively. Adjusting for 10% drop-out, 22 subjects will be enrolled in each arm.

13 Ethical considerations and administrative procedures

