2.5 Analysis of the primary objective

The primary objective of this study is to characterize those achieving seroprotection after receiving the 2020-2021 inactivated influenza vaccine in participants in all three cohorts. This will be achieved by estimating the seroprotection response rate.

A seroprotection responder is a participant achieving seroprotection as defined by a post-vaccination hemagluttination inhibition (HI) titer \geq 40.

The seroprotection response rate is defined as the proportion of participants with seroprotection.

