2.5.3 Handling of missing values/censoring/discontinuations

Non-responder imputation (NRI) for missing data will be applied. NRI is a conservative imputation method for dichotomous variables. NRI assumes that a participant is a treatment

failure if they discontinue the study prematurely. Hence, for missing data the primary variable outcome will be imputed to "No". Please refer to Appendix Section 5.1.3.3.

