5.4 Statistical models

Primary analysis

There is no hypothesis testing planned for this study.

Key secondary analysis

There is no key secondary analysis planned for this study.

Rule of exclusion criteria of analysis sets

Deviation ID	Description of deviation	Exclusion in analyses
INCL01A	No informed consent obtained or missing.	Exclude from the SAF.
INCL05	Not Planning to receive a 2020-2021 inactivated influenza vaccine	Exclude from the SAF
INCL06A	Not Planning to start treatment with ofatumumab for Cohort 1	Exclude from the SAF
INCL06B	Not already on commercially prescribed ofatumumab for Cohort 2 with minimum 4 weeks	Exclude from the SAF
INCL07	Currently not be receiving iDMT for Cohort 3	Exclude from the SAF

Analysis set	PD ID that cause participants to be excluded	Non-PD criteria that cause participants to be excluded
SAF	INCL01A	Influenza vaccine not taken
SAF	INCL05	Influenza vaccine not taken

Analysis set	PD ID that cause participants to be excluded	Non-PD criteria that cause participants to be excluded
SAF	INCL06A	Study treatment not taken
SAF	INCL06B	Study treatment not taken
SAF	INCL07	Study treatment not taken

6 Reference

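### Non-responder imputation is conservative for each cohort's own seroprotection rate but not for the iDMT reference side of the comparison, and the SAP leaves that reference shown under imputation alone

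*Protocol*

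**What the plan says.** **Missing-data rule.** Protocol 12.4.4: "Non-responder imputation approach will be applied to missing postvaccination antibody titer". SAP 2.5.3 and Appendix 5.1.3.3 repeat the rule, and SAP 2.5.3 adds that "NRI is a conservative imputation method for dichotomous variables". Neither document limits it to particular cohorts. SAP 2.5 sets the primary objective for the "inactivated influenza vaccine in participants in all three cohorts. This will be achieved by estimating the seroprotection response rate", so Cohort 3 is covered.

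**Role of Cohort 3.** The Protocol summary (Purpose and rationale) frames the question as adequacy of response "as measured by humoral responses compared to participants on an iDMT". Protocol 4.3 says that "a reference cohort of participants on iDMTs (interferon or glatiramer acetate) is included", because response varies with the strain.

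**What is estimated.** Protocol 12.4.2: "The 95% confidence interval for the proportion of responders will be calculated by using exact method". SAP 5.4: "There is no hypothesis testing planned for this study". Both documents also list fixed EMA thresholds, applied cohort by cohort (Protocol 12.5, SAP 2.7).

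**Observed data.** The protocol plans similar analyses of the primary endpoint on observed data. The sentence is run into the heading of 12.4.7, in the body and in the table of contents, but reads as the content of 12.4.6 (Supplementary analysis). SAP 2.5.4 plans no supportive analyses of the primary endpoint, and SAP Section 4 reports no change to protocol-specified analyses. For seroconversion, both documents plan imputed and observed-data results (Protocol 12.5, SAP 2.7.3).

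**Week 4 window.** SAP Tables 2-1 to 2-3 give study days 25 to 35 for Cohort 1, 22 to 42 for Cohort 2 and 25 to 31 for Cohort 3.

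**The concern.** Scoring a missing titer as failure can only lower a rate. For a cohort judged on its own rate or against a fixed threshold, that is the cautious direction. For a reference cohort it is not: a lower iDMT rate makes any given ofatumumab rate look better by comparison. The SAP's label, read without qualification, invites the reader to treat the imputed iDMT rate as a cautious benchmark.

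At stake is the descriptive reading of Cohorts 1 and 2 beside Cohort 3. With 22 participants per cohort, one imputed 'No' moves the denominator-based rate visibly. As the SAP stands, the seroprotection table would show only the imputed benchmark, with nothing beside it to reveal how much of a small gap comes from missing reference samples.

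**Working it through.** **Inputs.** 20 evaluable and 22 enrolled per arm, 10% drop-out in every arm, and response rates of 70%, 75% and 80% (Protocol 12.8.1). Rates from Protocol 1.1 for another anti-CD20 agent (55.5 to 80%) and healthy controls (75 to 97%) serve as stand-ins. Missingness by cohort is not in the documents and is assumed. Missingness is taken as unrelated to response.

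**The plan's own figures.** 1.96 × √(p(1−p)/20) gives 20.08, 18.98 and 17.53 points at 70%, 75% and 80%, matching the stated 20.1, 19 and 17.5. And 20 × 1.10 = 22. (The planned exact intervals are slightly wider: half-widths of about 21.2, 20.2 and 19.0 points.)

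**Formula.** Let p be the true rate and m the share of missing titers, with subscript 3 for iDMT and O for an ofatumumab cohort. The imputed rate is p(1−m), so

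imputed gap = p3(1−m3) − pO(1−mO) = (p3 − pO) − (p3·m3 − pO·mO).

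The displayed deficit is smaller than the true one only if p3·m3 > pO·mO. It is larger once mO/m3 exceeds p3/pO.

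**Two illustrations.**

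| Missing: iDMT / ofatumumab | 80% vs 70% (true gap 10) | 90% vs 70% (true gap 20) |
|---|---|---|
| 10% / 0% | 72 − 70 = 2 | 81 − 70 = 11 |
| 10% / 10% | 72 − 63 = 9 | 81 − 63 = 18 |
| 0% / 10% | 80 − 63 = 17 | 90 − 63 = 27 |

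The break-even ratio mO/m3 is 80/70 = 1.14 in the first column and 90/70 = 1.29 in the second. An observed-data analysis returns the true gap in every row, under the stated assumption.

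**Rates from Protocol 1.1.** Equal 10% missingness multiplies the gap by 0.9: 19.5 becomes 17.55 (75% vs 55.5%) and 17.0 becomes 15.3 (97% vs 80%). With 10% missing in Cohort 3 alone, the gaps become 67.5 − 55.5 = 12.0 and 87.3 − 80 = 7.3.

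**Counts.** Suppose 16 of 20 observed Cohort 3 participants respond: 80.0%, exact 95% CI 56.3 to 94.3. With two more enrolled but missing, imputation gives 16/22 = 72.7% (49.8 to 89.3), and scoring them 'Yes' gives 18/22 = 81.8%.
- Ofatumumab 14/20, none missing: the gap falls from 10.0 to 72.7 − 70.0 = 2.7 points.
- Two of 22 missing in both cohorts: 72.7 − 63.6 = 9.1.
- Two of 22 missing only on ofatumumab: 80.0 − 63.6 = 16.4.

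**If there is no true deficit.** With 75% in both and 10% missing only in Cohort 3, the table shows 67.5% against 75%: ofatumumab appears 7.5 points ahead.

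**Analysis window.** A titer drawn on day 33 counts as Week 4 in Cohorts 1 and 2. In Cohort 3 it lies beyond the last window and, as the tables read, would be missing and then 'No'. The SAP rule that combines windows for parameters not collected at every visit does not clearly rescue it, since no Cohort 3 window extends past day 31. The protocol's ±3 days around Week 4 is days 25 to 31, so only samples taken outside the visit window are affected.

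**The case against.** The strongest reply is that the label is correct for what is planned. Each cohort gets its own rate with an exact interval and is set against fixed thresholds. No between-cohort difference, margin or test exists, and neither document calls a comparison conservative. This stands: no formal conclusion is biased, and only the descriptive reading is affected.

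A reader might infer that the rule makes ofatumumab look closer to iDMT than it is. The documents do not support that as a fixed direction. The rule also lowers Cohorts 1 and 2, the planned drop-out is equal, and higher missingness on ofatumumab reverses the effect.

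A reader might also infer that Cohort 3 will have more missing titers because it is followed less closely. Against Cohort 2 this fails. Cohort 2 also has no study-supplied drug before Week 4 and no clinic visit between Screening and Week 4 (Protocol Section 8), and it has two scheduled home visits in that interval against three in Cohort 3. Cohort 3 lacks the optional extension, but that follows the primary titer. The unequal analysis windows are firmer ground, though they concern only late samples.

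Finally, the protocol already plans the observed-data analysis. True, and it would largely answer the point, but the SAP does not carry it for seroprotection. The SAP is written against protocol version 00, and the documents do not show whether that version contained the sentence, so its no-change statement may have been accurate then. It does not match the current protocol.

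**Conclusion.** The point holds as a matter of interpretation and reporting. The imputation is cautious for each cohort's own rate and not for the reference side of the comparison the study says it makes. At the planned equal 10% drop-out the effect is small, about a tenth of the gap (1 to 2 points in the cases above), against interval half-widths of roughly 20 points per cohort. It becomes material when missingness is unequal: two missing titers in Cohort 3 alone take a 10-point deficit to 2.7.

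These sizes rest on assumed rates, on assumed missingness by cohort, and on missingness unrelated to response. What does not rest on assumption is that the SAP, as written, offers no un-imputed seroprotection rate and closes the Week 4 window earliest in the reference cohort.

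**What to change.** 1. Keep non-responder imputation as the main rule. Add the observed-data analysis of seroprotection to the SAP for all three cohorts, with exact 95% intervals, so that it agrees with Protocol 12.4.6.
2. Report the number of missing Week 4 titers by cohort.
3. Beside the imputed Cohort 3 rate, show its rate with missing titers scored 'Yes' as a sensitivity bound. Add no rule for declaring the cohorts close, since the study is estimation only.
4. In SAP 2.5.3, restrict the word conservative to each cohort's own rate.
5. Use the same Week 4 analysis window for the titer in all three cohorts, so that a late Cohort 3 sample is not scored 'No' on a day that would count elsewhere.

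The cost is a few SAP sentences and table rows, with no new data. The downside is that the reference appears as a range instead of one number.

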12.4.5 Sensitivity analyses for primary endpoint/estimand

Not applicable.

12.4.6 Supplementary analysis

12.4.7 Similar analyses will be performed by using observed data. Supportive analyses

Not applicable.

12.5 Analysis of secondary endpoint(s)/estimand(s)

The secondary endpoint is achieving seroconversion defined as meeting one of the following two criteria:

- ≥ 4-fold increase in HI titers after vaccination (in participants with prevaccination HI titers ≥10) (yes/no) or
- postvaccination HI titers ≥40 (in participants with prevaccination HI titers < 10) (yes/no)

Proportion of participants achieved seroconversion at Week 4 will be estimated and the corresponding 95% confidence interval will be calculated using exact method.

Both non-responder imputation and observed case approaches will be applied in the analyses of seroconversion.

To assess the change in HI titers, geometric means will be calculated for pre- and post-vaccination HI titers.

To meet European Medicines Agency guidelines for protection for the Cohort, at least one of the following criteria has to be met:

- 1. Seroprotection rate is better than 70%;
- 2. Seroconversion rate is higher than 40%;
- 3. Ratio of geometric mean of post- to pre-vaccination HI titers ≥ 2.5 .

12.5.1 Efficacy and/or Pharmacodynamic endpoint(s)

Not applicable.

12.5.2 Safety endpoints

For all safety analyses, the safety set will be used. All listings and tables will be presented by treatment arm.

In particular, summary tables for adverse events (AEs) will summarize only on-treatment events, which started or worsened during the on-treatment period (treatment-emergent AEs).

Adverse events

All information obtained on adverse events will be displayed by treatment group and participant.

The number (and percentage) of participants with treatment emergent adverse events (events started after the first dose of study medication or events present prior to start of double-blind treatment but increased in severity based on preferred term) will be summarized in the following ways:

- by treatment, primary system organ class and preferred term.
- by treatment, primary system organ class, preferred term and maximum severity.
- by treatment, Standardized MedDRA Query (SMQ) and preferred term.

Separate summaries will be provided for study medication related adverse events, death, serious adverse events, other significant adverse events leading to discontinuation, and adverse events leading to dose adjustment.

In addition, a separate listing of death including on treatment and post treatment deaths will be provided.

Clinical laboratory evaluations

All laboratory data will be listed by treatment arm, participant, and visit/time and if normal ranges are available abnormalities will be flagged. Summary statistics will be provided by treatment arm and overall. Shift tables using the low/normal/high/ (low and high) classification will be used to compare baseline to the worst on-treatment value.

12.6 Analysis of exploratory endpoints

Not applicable.

12.7 Interim analyses

For the purpose of early dissemination of results, two interim analyses will be performed after:

- on/around April 12, 2021, whichever comes first.
- on/around March 31, 2022, whichever comes first.

At the time of each interim analysis, methods proposed in Sections 12.5 and 12.6 for data summary and analyses will be performed. Since there will be no hypothesis testing involved, statistical adjustment for the interim analyses will not be made at the stage of final analyses of efficacy and safety.

Page 49 of 51

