4.4 Purpose and timing of interim analyses/design adaptations

For the purpose of earlier dissemination of results, an interim analysis will be performed after either all enrolled participants have completed or discontinued the Investigational Period or on/around March 31, 2022, whichever comes first.

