The study population will consist of male and female participants, \geq 18 years of age to 55 years of age inclusive, with a diagnosis of relapsing MS.

The study aims to enroll up to 66 participants (up to 22 participants per cohort) at approximately 12 centers in the United States. Since a 25% screen failure rate is expected, approximately 88 participants will be screened.

The last day to screen a patient for this study will be when Cohort 1 and Cohort 3 each have 22 participants enrolled, or at the end of Q1 2023, whichever comes first.

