2.2 Analysis sets

Safety set

The Safety Set (SAF) comprises all participants who have received the 2020-2021 inactivated influenza vaccine.

Unless stated otherwise, the SAF will be used for all summary tables and listings.

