2.14 Interim analysis

For the purpose of earlier dissemination of results, an interim analysis will be performed after:

- all enrolled participants have completed the Investigational Period or discontinued the Investigational Period prematurely OR
- On/around March 29, 2021, whichever comes first.

Since there will be no hypothesis testing involved, statistical adjustment for the interim analysis will not be made at the stage of final analyses.

3 Sample size calculation

Sample size calculations were based on the proportion of participants who responded to influenza vaccination.

The sample size of 20 participants per arm is selected based on budget and need for early availability of results. The sample size of 20 subjects will provide estimates with margin of error (half-width of a 95% confidence interval) of 20.1%, 19%, and 17.5% corresponding to response rates of 70%, 75%, and 80%, respectively. Adjusting for 10% drop-out, 22 subjects will be enrolled in each arm.

4 Change to protocol specified analyses

There are no changes to protocol specified analyses.

5 Appendix

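### At the date-triggered interims, the non-responder rule as written would count vaccinated participants not yet due at Week 4 as non-responders; the plan needs an interim evaluable set

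*Protocol*

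**What the plan says.** **Timing.** Protocol 12.7 plans two interims for early dissemination, one "on/around April 12, 2021, whichever comes first" and one "on/around March 31, 2022, whichever comes first". In the text available, both bullets keep the comparative ending but name no alternative to the date. Protocol 4.4 does name one for 2022: all enrolled participants having "completed or discontinued the Investigational Period or on/around March 31, 2022, whichever comes first". SAP 2.14 plans a single interim with the same alternative, or "On/around March 29, 2021, whichever comes first".

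**Enrolment.** Protocol Section 5 allows screening until Cohorts 1 and 3 each have 22 enrolled "or at the end of Q1 2023, whichever comes first". Amendment 3 extended the study because enrolment was not expected to be complete.

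**Missing titers.** Protocol 12.4.4: "Non-responder imputation approach will be applied to missing postvaccination antibody titer". SAP 2.5.3 first explains NRI by premature discontinuation and then states the operative rule: "Hence, for missing data the primary variable outcome will be imputed to" a negative response. SAP 5.1.3.3 repeats both parts. For seroconversion, Protocol 12.5 and SAP 2.7.3 use NRI and observed data, and the SAP lets the NRI result lead.

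**Denominator.** SAP 2.2 defines the Safety Set as everyone who received the 2020-2021 vaccine and adds: "Unless stated otherwise, the SAF will be used for all summary tables and listings". A Week 4 visit is not required. Protocol 12.1 defines its Safety Set by a dose of study drug and assigns it to demography, baseline and safety. It names no set for the response rates.

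Neither document defines an interim evaluable set, or says what to do with a participant whose Week 4 visit is still ahead.

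**The concern.** Vaccination comes before or at Week 0 and the titer is drawn at Week 4, so anyone vaccinated in roughly the last month before a calendar cut has no post-vaccination titer yet. That absence is administrative. It says nothing about the immune response, and it is not the premature discontinuation that the SAP gives as its reason for NRI. The rule itself is nevertheless worded for every missing titer.

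The interims exist to release results early, so the interim rate is itself the product. If pending participants stay in the denominator as failures, the rate depends on how many people happened to be vaccinated just before the cut. The shift is always downward. It would differ between cohorts with different late recruitment, which would disturb the reading of the ofatumumab cohorts against the iDMT reference cohort.

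**Working it through.** **The plan's own precision figure.** Protocol 12.8.1 gives margins of 20.1%, 19% and 17.5% for n = 20 at rates of 70%, 75% and 80%. The Wald half-width 1.96 × √(p(1−p)/20) gives 20.08%, 18.98% and 17.53%, so the figures reproduce.

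**Who would be pending.** The SAP visit-window tables put Week 0 on Day 1 and Week 4 on Day 28. A participant whose Week 0 falls after 4 March 2022 has not reached Day 28 by 31 March 2022. For a 12 April 2021 cut the corresponding date is 16 March 2021. Vaccinated participants still waiting for Week 0 are pending too.

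**Effect.** Let n be the number vaccinated, k the number pending and p the true response rate, with no other titers missing. With pending participants scored as non-responders, the expected rate is p × (n − k)/n. The documents do not give k, so it is an assumption here.

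| n | k | p = 70% | p = 75% | p = 80% |
|---|---|---|---|---|
| 22 | 0 | 70.0 | 75.0 | 80.0 |
| 22 | 1 | 66.8 | 71.6 | 76.4 |
| 22 | 2 | 63.6 | 68.2 | 72.7 |
| 22 | 3 | 60.5 | 64.8 | 69.1 |
| 10 | 1 | 63.0 | 67.5 | 72.0 |
| 10 | 2 | 56.0 | 60.0 | 64.0 |

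For example, 75% × 20/22 = 68.2%. The rows with n = 10 (assumed) stand for a single enrolment-year row, which Protocol 12.4.2 requires and where denominators are smaller.

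**Share pending that brings the expected rate down to 70%.** This is 1 − 70/p: 6.7% of those vaccinated if p = 75%, and 12.5% if p = 80%.

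**One realised table (assumed counts, exact intervals).** Suppose 15 of 20 assessed participants respond and 2 more are pending. Leaving the pending out gives 15/20 = 75.0% (95% CI 50.9 to 91.3). Scoring them as non-responders gives 15/22 = 68.2% (45.1 to 86.1). The 6.8-point shift is about a third of the plan's 19-point margin (6.8/19 = 0.36).

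**Season row against overall row.** Assume uniform accrual over a 26-week season and 4 weeks from vaccination to titer, with the cut at the season's end. Then 4/26 = 15.4% of that season's participants are pending, and 75% reads 63.5%. Seasons of 20 to 30 weeks with lags of 5.5 to 3 weeks give 75% × (1 − 5.5/20) = 54.4% up to 75% × (1 − 3/30) = 67.5%. Pooling two equal 26-week seasons, with the first fully assessed, gives 4/52 = 7.7% pending, and 75% reads 69.2%. Recruitment may thin out late in the season, so these are illustrations and not forecasts.

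**The case against.** A reader might infer that the plan reports pending participants as vaccine failures. The documents do not say so. SAP 2.5.3 and 5.1.3.3 tie NRI to premature discontinuation, a pending participant has not discontinued, and a careful programmer could leave such people out. That stands against any claim of certainty. It does not close the gap, because the operative sentences cover all missing titers without exception.

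Protocol 12.7 applies Sections 12.5 and 12.6 at the interims and does not cite 12.4, where the primary NRI rule sits. This also stands, in part. But 12.5 itself prescribes NRI for seroconversion and uses the seroprotection rate in its 70% criterion, 12.6 is marked not applicable, and SAP 2.14 has no such restriction. The reference looks like a numbering slip.

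Observed-data results are planned: for seroprotection in Protocol 12.4.6 and its run-on heading 12.4.7, and for seroconversion in both documents. They give a rate free of this bias. However, SAP 2.5.4 plans no supportive analysis of the primary endpoint, and NRI leads for seroconversion.

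The SAP was written for protocol version 00 and the 2020-2021 vaccine, so for the second interim its denominator is carried over by inference. That is correct, and it means that no current text governs that interim.

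A reader might also infer that a rate pushed below 70% fails a cohort or damages the trial's conclusions. Neither follows. The criteria in Protocol 12.5 need only one of three to be met, and the geometric-mean ratio has no NRI rule. No hypothesis is tested, there is no study stopping rule, and the final analysis uses all data at trial end.

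**Conclusion.** The concern holds as a literal reading of a stated rule. Date-triggered interims with enrolment possibly open, an all-vaccinated denominator and unconditional imputation of missing titers together would count participants not yet due at Week 4 as non-responders. The rationale given for NRI does not cover them.

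The size depends on an unknown. At 22 vaccinated and a true rate of 75%, one pending participant costs 3.4 points (75.0 − 71.6) and two cost 6.8. The bias is largest in the current-season row and smaller in the overall rate at the second interim. It is zero if nobody is pending, including when the all-completed-or-discontinued trigger comes first. It is confined to descriptive interim tables and is partly mitigated by the observed-data analyses. The conclusion assumes that NRI is used for the interim rates and that the all-vaccinated set carries over to the later seasons.

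**What to change.** State in Protocol 12.7 and SAP 2.14 that interim seroprotection and seroconversion rates are computed in vaccinated participants whose Week 0 date is early enough for the protocol Week 4 visit, including its +3 days, to fall on or before the data cut-off, whether or not they discontinued. Taking Week 4 as Day 28, the limit is Day 31: Week 0 by 1 March 2022 for a 31 March 2022 cut, or by 13 March 2021 for a 12 April 2021 cut.

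Apply NRI only within that set, report the observed-data rate beside it, and show the number pending by cohort and enrolment year. Membership should depend on the Week 0 date alone. Counting discontinuers at once while waiting for everyone else's analysis window to close (Day 42 for Cohort 2 in the SAP) would introduce a downward bias of its own.

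At the same time, correct the 12.7 cross-reference to 12.4 and 12.5, complete its two bullets, and align the SAP's interim section and analysis set with the amended protocol.

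The cost is a few sentences and one programming flag. The downside is a slightly smaller interim denominator and wider interim intervals.

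### Protocol 12.7 sends the interim analyses to Sections 12.5 and 12.6 and omits 12.4, so as written they do not call the primary seroprotection analysis

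*Protocol*

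**What the plan says.** **Methods at the interims.** Protocol 12.7 gives early dissemination of results as the purpose of two interim analyses and then says: "At the time of each interim analysis, methods proposed in Sections 12.5 and 12.6 for data summary and analyses will be performed". It adds that no adjustment will be made, because nothing is tested.

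**Where the methods are.** Protocol 12.4 is the primary analysis. Section 12.4.2 says "The number and percentage of responders by year of enrolment in study and overall will be presented", with an exact 95% confidence interval. Section 12.4.4 says "Non-responder imputation approach will be applied to missing postvaccination antibody titer". The supplementary-analysis item at the end of 12.4 adds an observed-data version. Protocol 12.5 covers seroconversion, geometric mean titers, the EMA criteria and, in 12.5.2, safety. The next section is headed "12.6 Analysis of exploratory endpoints", and its only content is that it does not apply.

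**Timing.** Protocol 4.4 says "an interim analysis will be performed after either all enrolled participants have completed or discontinued the Investigational Period or on/around March 31, 2022", whichever is earlier. Protocol 12.7 lists two interims. The first is "on/around April 12, 2021, whichever comes first", and the second has the same form with March 31, 2022. SAP 1.1 and 2.14 plan one interim, triggered by all participants finishing or leaving the Investigational Period or by March 29, 2021, whichever is earlier. SAP Section 1 says that it follows protocol version 00.

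**The concern.** Of the two sections named in 12.7, one is empty and the other is not the primary analysis. A programmer or medical writer who follows the text literally would produce seroconversion, geometric means, the EMA criteria and safety, without the analysis that answers the primary objective.

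The interims exist so that results can be released before the study ends. If the plan does not fix what is reported on the primary endpoint, then the interval, the missing-data rule and the split by year are chosen in an open-label study with the accumulating data in view.

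The timing text has a related gap. In 12.7 each interim has a date and a clause about which event is earlier, but no second event to compare with the date. Sections 4.4 and 12.7 and the SAP also do not list the same interims.

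**Working it through.** **Step 1: follow the references in Protocol 12.7.**

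- 12.5: seroconversion with an exact 95% interval, under both non-responder imputation and observed cases; geometric means; EMA criteria; safety.
- 12.6: nothing to perform.
- 12.4: not cited.

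**Step 2: list what 12.4 contains and see whether 12.5 supplies it for seroprotection.**

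- Seroprotection rate: appears in 12.5 only as an EMA criterion (above 70%).
- Exact 95% interval: given in 12.5 for seroconversion only.
- By-year and overall presentation: not in 12.5.
- Non-responder imputation and observed-data analysis: given in 12.5 for seroconversion only.

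A literal reading of 12.5 therefore yields a seroprotection percentage per cohort, with no interval, no missing-data rule and no split by year.

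**Step 3: look for text elsewhere that fills the gap.** Protocol 4.4 gives purpose and timing. SAP 1.1 and 2.14 give timing, and 2.14 also gives the purpose and the absence of adjustment. None names an endpoint or a method section for the interim. SAP 2.5 specifies a primary analysis but does not say that it is run at the interim.

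**Step 4: what a bare rate would leave out.** Protocol 12.8.1 gives 95% half-widths of 20.1%, 19% and 17.5% at rates of 70%, 75% and 80% with 20 participants. The normal approximation 1.96 × √(p(1−p)/20) gives 20.08%, 18.98% and 17.53%, so those figures reproduce. The exact (Clopper-Pearson) intervals, one implementation of the exact method that 12.4.2 calls for, are:

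- 14/20 = 70%: 45.7% to 88.1%
- 15/20 = 75%: 50.9% to 91.3%
- 16/20 = 80%: 56.3% to 94.3%

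All three contain the 70% EMA threshold, so a percentage above 70% says little without its interval. Interim cohorts may be smaller than 20.

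The missing-data rule matters too. As an illustration, assume a cohort of 22 with 2 missing titers (22 − 20 = 2, the planned drop-out allowance) and 15 responders. Observed cases give 15/20 = 75.0%. Non-responder imputation gives 15/22 = 68.2%. The two results fall on opposite sides of 70%, and 12.5 does not say which applies to seroprotection.

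**Step 5: compare the timing text.**

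- Protocol 4.4: one interim; event or March 31, 2022.
- Protocol 12.7: two interims; April 12, 2021 and March 31, 2022; no event for either.
- SAP 1.1 and 2.14: one interim; event or March 29, 2021.

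The 2022 date agrees between 4.4 and 12.7. The 2021 date differs by 14 days (March 29 to April 12) between the SAP and 12.7.

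**The case against.** The strongest reply is that this is a slip with little effect. The interims are for dissemination, and the same paragraph of 12.7 goes on to mention final analyses of efficacy and safety. SAP 2.14 does not restrict the interim to secondary endpoints, and SAP 2.5 sets out a primary analysis. Most teams would report seroprotection anyway. No test, stopping rule or adjustment depends on the interims, and Protocol Section 12 places the analysis on all participant data at the end of the trial.

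Most of this stands. A reader might infer that the sponsor chose to leave the primary endpoint out of the interims; no text supports that. A reader might also infer that no seroprotection result would appear at all. That goes too far, because the EMA criterion in 12.5 needs the rate.

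On timing, a reader might take 4.4 and 12.7 as rival plans. The Amendment 3 rationale says that a second interim was added, and 4.4 carries the same 2022 date as 12.7, so 4.4 is better read as not updated. The event trigger is also not lost from the documents: 4.4 keeps it for the 2022 interim and the SAP keeps it for the 2021 one.

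What the reply does not remove is that 12.7 is the operative text, it is wrong as written, and correcting it means inferring intent that is stated nowhere.

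**Conclusion.** The point holds as an error in operative text. Protocol 12.7 does not call the primary analysis at either interim. The missing elements are the exact 95% interval, the by-year and overall presentation, non-responder imputation and the observed-data analysis; a bare seroprotection rate could still appear through 12.5. That the intended reference was 12.4 and 12.5 is likely but is an inference.

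The effect is confined to what is reported at the interims and how clearly. It would be wrong to infer any harm to the final analysis, the error rates or the sample size: no hypothesis test is planned, and correcting the reference changes none of these. The available text does not date Amendment 3. If the first interim had already been run, the correction matters mainly for the second.

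The timing differences are a secondary matter of alignment. They should be settled in the same edit but do not add to the seriousness of the main point.

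**What to change.** **Main change.** In Protocol 12.7, replace the reference to Sections 12.5 and 12.6 with Sections 12.4 and 12.5 (including 12.5.2). State the same in SAP 2.14, which at present names no interim endpoints or methods.

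**Timing, in the same edit.** List the same two interims, with the same dates, in Protocol 4.4, Protocol 12.7, SAP 1.1 and SAP 2.14, and settle the 2021 date. In 12.7, either delete the clause about whichever comes first or give each interim its own alternative event. Do not put the trigger that all enrolled participants have finished or left the Investigational Period in both bullets: if that event came first, both interims would fire together.

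**Cost.** Wording only. No new data are needed, and no programming beyond what the final analysis already requires.
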